13.1.4 Hospitalization

Any inpatient hospital admission that includes a minimum of an overnight stay to a healthcare facility meets the criteria for ‘hospitalization’. Admission also includes transfer within the hospital to an acute/intensive care unit (e.g., from the psychiatric wing to a medical floor, medical floor to a coronary care unit, neurological floor to a tuberculosis unit).

The following are not considered to be hospitalization:

- Rehabilitation facilities.
- Hospice facilities.
- Respite care (e.g., caregiver relief).
- Skilled nursing facilities.
- Nursing homes.
- Routine emergency room admissions.
- Same day surgeries (as outpatient /same day/ambulatory procedures).

Hospitalization or prolongation of hospitalization in the absence of a precipitating, clinical AE is not in itself a SAE. Examples include:

- Admission for treatment of a preexisting condition not associated with the development of a new AE or with a worsening of the preexisting condition (e.g., for work-up of persistent pre-treatment lab abnormality).
- Social admission (e.g., patient has no place to sleep).
- Administrative admission (e.g., for yearly physical examination).
- Protocol-specified admission during a study (e.g., for a procedure required by the study protocol).
- Optional admission not associated with a precipitating clinical AE (e.g., for elective cosmetic surgery).
- Hospitalization for observation without a medical AE.
- Pre-planned treatments or surgical procedures should be noted in the baseline documentation or the entire protocol and/or for the individual patient.
- Admission exclusively for the administration of blood products.

Diagnostic and therapeutic non-invasive and invasive procedures, such as surgery, should not be reported as AEs. However, the medical condition for which the procedure was performed should

be reported if it meets the definition of an AE. For example, an acute appendicitis that begins during the AE reporting period should be reported as the AE, and the resulting appendectomy should be recorded as treatment of the AE.

13.1.5 Suspected Unexpected Serious Adverse Reaction

Suspected Unexpected Serious Adverse Reactions (SUSAR) are events which are serious as per the above criteria, the nature or severity of which is not consistent with the applicable product information (e.g., current Investigator's Brochure) and are judged by the Investigator or by the Sponsor to be related to investigational product. For a non-Sponsored investigational product (e.g., a comparator product) with a marketing authorization, the expectedness of an AE will be determined by whether or not it is listed in the package insert/SPC.

13.1.6 Severity Assessment

Adverse events will be graded by the Investigator according to the NCI CTCAE v.4.03 (Publish Date: June 14, 2010, <http://ctep.cancer.gov/reporting/ctc.html>), according to the following general categories:

Grade 1:	Mild; asymptomatic or mild symptoms; clinical or diagnostic observations only; intervention not indicated.
Grade 2:	Moderate; minimal, local or noninvasive intervention indicated; limiting age-appropriate instrumental activities of daily living.
Grade 3:	Severe or medically significant but not immediately life-threatening; hospitalization or prolongation of hospitalization indicated; disabling; limiting self-care activities of daily living.
Grade 4:	Life-threatening consequences; urgent intervention indicated.
Grade 5:	Death related to AE.

Note the distinction between the severity and the seriousness of an AE. A severe event is not necessarily a serious event. For example, a headache may be severe (interferes significantly with patient's usual function) but would not be classified as serious unless it meets one of the criteria for SAEs, listed above.

13.1.7 Causality Assessment

The Investigator's assessment of causality must be provided for all AEs (serious and non-serious); the Investigator must record the causal relationship in the CRF and report such an assessment in accordance with the serious adverse reporting requirements, if applicable. A

suspected adverse reaction means any AE for which there is a reasonable possibility that the investigational product caused the AE. An Investigator's causality assessment is the determination of whether there exists a reasonable possibility that the investigational product caused or contributed to an AE; generally the facts (evidence) or arguments to suggest a causal relationship should be provided. If the Investigator does not know whether or not the investigational product caused the event, then the event will be handled as "related to investigational product" for reporting purposes, as defined by the Sponsor (see Section on Reporting Requirements). If the Investigator's causality assessment is "unknown but not related to investigational product", this should be clearly documented on study records.

For all AEs, sufficient information should be obtained by the Investigator to determine the causality of the AE (e.g., investigational product or other illness). The relationship of the AE to the study treatment (investigational product, comparator or placebo [as applicable]) will be assessed following the definitions below:

- 'No' (unrelated): Any event that does not follow a reasonable temporal sequence from administration of investigational product AND is likely to have been produced by the patient's clinical state or other modes of therapy administered to the patient.
- 'Yes' (related): Any reaction that follows a reasonable temporal sequence from administration of investigational product AND follows a known response pattern to the suspected investigational product AND recurs with re-challenge, AND/OR is improved by stopping the investigational product or reducing the dose.

In addition, if the Investigator determines an AE is associated with study procedures, the Investigator must record this causal relationship on the AE CRF page and report such an assessment in accordance with the SAE reporting requirements, if applicable.

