Starting Dose	2000 mg/m ² , 1000 mg/m ² BID
-1	1500 mg/m ² , 750 mg/m ² BID
-2	1000 mg/m ² , 500 mg/m ² BID

Abbreviation: BID: twice daily

If doses of investigational product are held, study procedures for that cycle will proceed on schedule as planned, without any delay. This also applies to tumor assessments, which should continue to be done every 6 weeks, starting from the first dose of investigational product until the first planned tumor assessment at 6 weeks (± 3 days), and then after every subsequent 6 weeks (± 3 days) of treatment regardless of any changes in dose or occurrence of AEs. Missed dose(s) of investigational product (i.e., any dose that is not administered within the protocol-defined administration window) will not be made up. The dose adjustment guidelines represent the minimum set of measures that Investigators must follow. However, additional measures may be taken, as necessary, for certain patients per the Investigator's medical judgment. All dose modifications/adjustments should be documented in the patient's source file.

Once an investigational product dose has been reduced for a patient, all subsequent cycles must be administered at that dose, unless further dose reduction is required. Dose re-escalation is not permitted.

Patients must discontinue an investigational product if a criterion for investigational product withdrawal is met (see Section 10.1 and Appendix 2).

Once an investigational product has been discontinued, patients who had been receiving combination therapy may continue to receive the other investigational product as monotherapy, at the Investigator's discretion. This is applicable to both treatment arms of the study. Reintroduction of the discontinued investigational product at a later time during the active treatment phase is not permitted.

Detailed rules for dose adjustments of neratinib, lapatinib, and capecitabine in case of toxicity are provided in Appendix 2.

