9.3. Adverse Events, Serious Adverse Events, and Deaths

All AEs and SAEs will be reported until 28 days after the last dose of investigational product(s) and will be followed until resolution or until condition stabilizes. Should an Investigator be made aware of any SAE occurring any time after the reporting period, it must be promptly reported. The Patient Diary used for recording of investigational product intake will also be used by patients to document any AEs experienced during study treatment. In the case of diarrhea, it also serves to document the number of loose stools per day and use of loperamide/other antidiarrheal treatments taken.

AEs and SAEs will be coded using the most current version of MedDRA and tabulated by system organ class (SOC) and preferred term (PT). All AEs will be graded by the Investigator according to the NCI CTCAE v.4.0. Summaries will in general focus on treatment emergent adverse events (TEAEs). A TEAE is any adverse event that occurs or worsens on or after first dose of investigational product and up to 28 days after the last dose.

TEAEs and SAEs will be tabulated by SOC, PT, and treatment group. All tabulations will be sorted by descending frequency of SOC and PT in the total column unless otherwise noted. TEAEs will also be summarized according to relationship to study drug and severity. TEAEs of toxicity grade 3 or higher will also be summarized.

Similarly, treatment emergent adverse events leading to treatment discontinuation, dose modification, dose hold, and/or delay of investigational product will be tabulated by SOC, PT and treatment group.

Separate summaries and comparisons between treatment groups will be presented for treatment emergent diarrhea events leading to treatment discontinuation, dose holds, dose reductions, and delay of investigational product. Therapies used to treat diarrhea will also be summarized using descriptive statistics and compared between treatment groups.

SAEs, and TEAEs will be listed in by patient listings sorted by treatment, patient ID and study day; SAEs will be flagged. All AE listings will include study day, SOC, PT, reported term, dose, Cycle/day, AE onset date, AE resolution date, outcome, duration, relationship to drug, action taken, and severity.

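### Protocol 13.1.7 sets a reasonable-possibility standard for causality, then Yes/No definitions that are narrower and leave some events in neither category

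*Protocol*

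**What the plan says.** Protocol 13.1.7 requires the investigator to give a causality assessment for every adverse event, serious or not. Its general standard is broad: a "suspected adverse reaction means any AE for which there is a reasonable possibility that the investigational product caused the AE". An investigator who does not know the cause has the event treated as related for reporting purposes.

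The section then says that the relationship "will be assessed following the definitions below", and gives two.

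- *Yes* starts with timing and pattern: "Any reaction that follows a reasonable temporal sequence from administration of investigational product AND follows a known response pattern to the suspected investigational product". A last clause, on re-exposure and withdrawal, is joined to these two conditions: "AND recurs with re-challenge, AND/OR is improved by stopping the investigational product or reducing the dose".
- *No* is also a joint condition: "Any event that does not follow a reasonable temporal sequence from administration of investigational product AND is likely to have been produced by" something else, namely the underlying condition or a different treatment.

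Protocol 13.1.5 defines a SUSAR as a serious event, "the nature or severity of which is not consistent with the applicable product information", that the investigator or the sponsor judges to be related. On re-exposure, Protocol 6.1.3 states: "Reintroduction of the discontinued investigational product at a later time during the active treatment phase is not permitted".

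In the analysis, SAP 9.3 states that "TEAEs will also be summarized according to relationship to study drug and severity". SAP section 12 plans the matching table, and section 14 plans a listing of drug-related events.

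**The concern.** The wording that introduces the two definitions makes them the operative rule, not examples. They ask for much more than a reasonable possibility. A reaction not seen before has no known pattern to follow. A patient who dies in a first episode can neither improve on stopping nor show recurrence. These are reactions that a causality assessment ought to be able to capture.

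Sites that follow the general sentence and sites that follow the definitions could code the same event differently. With about 200 centers planned, that would put noise into every output that depends on the relationship field. The investigator's judgement is also one of the two routes by which an event becomes a SUSAR.

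**Working it through.** No arithmetic applies, so the wording is checked as logic. All conditions come from Protocol 13.1.7:

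- A: plausible timing
- B: known response pattern
- C: recurs on re-challenge
- D: improves on stopping or dose reduction
- E: another cause is likely

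The AND/OR in the *Yes* definition allows two readings.

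- Natural reading: *Yes* = A and B and (C or D)
- Loose reading: *Yes* = (A and B and C) or D
- *No* on both readings = (not A) and E

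| Event | A | B | C | D | Natural reading | Loose reading | Meets *No*? |
|---|---|---|---|---|---|---|---|
| Known pattern, improves on hold | true | true | false | true | Yes | Yes | no |
| No known pattern, improves on stopping | true | false | false | true | not Yes | Yes | no |
| No known pattern, does not improve | true | false | false | false | not Yes | not Yes | no |
| Fatal first episode, known pattern | true | true | false | false | not Yes | not Yes | no |
| Fatal after an earlier episode that recurred on resumption, known pattern | true | true | true | false | Yes | Yes | no |

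Three results follow.

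1. With B false, the natural reading never gives *Yes*. The loose reading gives it only when the event improves on stopping or dose reduction.
2. With C and D both false, neither reading gives *Yes*. That covers every fatal reaction with no earlier episode.
3. With A true, *No* always fails, whatever the value of E. The third and fourth rows therefore fit neither category on either reading, and the second fits neither on the natural reading. So does an event with plausible timing, no known pattern, no improvement and an evident other cause.

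Condition C is hard to observe after permanent discontinuation, because 6.1.3 bars reintroduction. It is not always unobservable: Appendix 2 (for example Tables A2.1 and A2.8) provides for holding, resuming and second appearances, so some dechallenge and re-challenge information will exist.

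**The case against.** A reader might infer that a new or fatal reaction can never be called related, and that SUSARs will therefore be missed. The documents do not support that.

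- On the loose reading, a new reaction that improves on stopping is *Yes*. A fatal event after an earlier episode can qualify. A SUSAR may be unexpected in severity alone and still follow a known pattern.
- Protocol 13.3 sends all serious events to the sponsor within 24 hours irrespective of relationship. Under 13.1.5 the sponsor's own judgement of relatedness is sufficient, and 13.5 makes the sponsor responsible for SUSAR reporting.
- Where neither definition fits, an investigator may reasonably say that the cause is unknown, and 13.1.7 then treats the event as related for reporting. Such events cannot properly be coded *No* either, so under-counting is not established.
- Follow-up does not clearly depend on relatedness. Protocol 13.2 says only that follow-up of related events may be required, while Protocol 12.4.2 and SAP 9.3 follow events to resolution or stabilization without that limit.
- The main safety outputs (all TEAEs, SAEs, grade 3 or higher, discontinuations, deaths) do not filter on relationship.

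These points stand, and they limit the finding. They do not remove it. The unknown-cause default is worded for reporting and does not say how the CRF field is completed; the next sentence even allows an entry of unknown but not related. For non-serious events the documents describe no second causality judgement. The reasonable-possibility sentence is one side of the contradiction, so it cannot settle it.

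**Conclusion.** The concern holds as an internal contradiction in Protocol 13.1.7. The Yes/No definitions are narrower than the section's own standard, and together they leave some events unclassified although an answer is mandatory. The consequences are inconsistent coding between sites, a TEAE-by-relationship table and drug-related listing that cannot be relied on, and a weakened investigator route to a SUSAR. It is not a failure of SUSAR reporting, and it does not touch the co-primary endpoints.

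The size is logical, not numeric. The pneumonitis and lung-infiltration rates in Appendix 2 (0.6% and 0.4%) might tempt a reader to estimate a count. They are all-case rates on neratinib monotherapy, and those cases were considered drug-related, so they do not measure misclassification. A reader might also expect the known-pattern condition to weigh more on neratinib than on the marketed comparator. The documents give nothing to test that, so the direction of any difference between arms stays open.

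The conclusion assumes that at least some sites apply the definitions as written. The CRF completion instructions are not among the documents and could already use different wording.

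**What to change.** In Protocol 13.1.7, and in identical words in the CRF completion guide:

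- Define *Yes* as a reasonable possibility that the investigational product caused or contributed to the event.
- Define *No* as its complement: no such reasonable possibility. Every event then has exactly one answer.
- List timing, known response pattern, dechallenge and re-challenge as considerations that inform the judgement, not as required conditions.

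The cost is a few lines of text. No dose, schedule, endpoint or analysis method changes. The downside is that slightly more events will be coded as related.

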13.1.8 Special Reporting Situations

Safety events of interest on the Sponsor's investigational product that may require expedited reporting and/or safety evaluation include, but are not limited to:

- Overdose of an investigational product.
- Suspected abuse/misuse of an investigational product.
- Inadvertent or accidental exposure to an investigational product.
- Medication error that may result from the administration or consumption of the wrong drug, by the wrong patient, at the wrong time, or at the wrong dosage strength.
- Suspected transmission via an investigational product of an infectious agent.

Special reporting situations should be recorded on the AE CRF page. Any special reporting situation that meets the criteria of a SAE should be recorded on the SAE form and reported as required (see Section 13.3).

13.2 Reporting Adverse Events

For serious and non-serious AEs, the reporting period to the Sponsor (or its designated representative) begins from the time that the patient provides informed consent, which is obtained prior to the patient's participation in the study, i.e., prior to undergoing any study-related procedure and/or receiving investigational product, through 28 calendar days after the last administration of the investigational product.

For all AEs with causal relationship to the investigational product, follow-up by the Investigator may be required until the event or its sequelae resolve or stabilize at the level acceptable to the Investigator, and the Sponsor concurs with that assessment.

If a patient begins a new anticancer therapy, the AE reporting period for non-serious AEs ends at the time the new treatment is started. Death must be reported if it occurs during the SAE reporting period after the last dose of investigational product, irrespective of any intervening treatment.

The Sponsor will evaluate any safety information that is spontaneously reported by an Investigator beyond the time frame specified in the protocol.

13.3 Reporting Serious Adverse Events

All SAEs, irrespective of relationship to investigational product, must be reported within 24 hours of discovery or notification of the event to the Sponsor or designated representative using the SAE form. The SAE form must be signed by the Investigator. In particular, if the SAE is fatal or life-threatening, notification to the Sponsor must be made immediately, irrespective of the extent of available AE information. This timeframe also applies to follow-up information on previously forwarded SAE reports as well as to the initial and follow-up reporting of exposure during pregnancy and exposure via breast feeding cases. For SAE reporting information, please refer to the Study Contact List which is provided as a separate document.

Relevant medical records should be provided to the Sponsor or its designated representative as soon as they become available; autopsy reports should be provided for deaths if available.

Should an Investigator be made aware of an SAE occurring any time after the reporting period, it must be promptly reported.

All SAEs that have not resolved by the end of the study, or that have not resolved upon discontinuation of the patient's participation in the study, must be followed until any of the following occurs:

- The event resolves.
- The event stabilizes.
- The event returns to baseline, if a baseline value/status is available.
- The event can be attributed to agents other than the investigational product or to factors unrelated to study conduct.
- It becomes unlikely that any additional information can be obtained (patient or health care practitioner refusal to provide additional information, lost to follow-up after demonstration of due diligence with follow-up efforts).

13.4 Pregnancy

All initial reports of pregnancy must be reported to the Sponsor by the investigational staff within 24 hours of their knowledge of the event using the appropriate Exposure-In-Utero (EIU) form.

For investigational products and for marketed products used as investigational product in neratinib studies, an exposure during pregnancy occurs if:

- A female becomes, or is found to be, pregnant either while receiving or having been directly exposed (e.g., environmental exposure) to the investigational product, or the female becomes, or is found to be, pregnant after discontinuing and/or being directly exposed to the investigational product (maternal exposure) for 28 days after last dose of or exposure to investigational product.
- A male partner of a pregnant female has been exposed to the investigational product, either due to treatment or environmental exposure, within 3 months prior to the time of conception and/or is exposed during his partner's pregnancy (paternal exposure).

If any study patient or study patient's partner becomes or is found to be pregnant during the study patient's treatment with the investigational product or exposure as defined above, the Investigator must submit this information on an EIU form to the Sponsor (or its designated representative). In addition, the Investigator must submit information regarding environmental exposure to an investigational product in a pregnant woman (e.g., a patient reports that she is pregnant and has been exposed to a cytotoxic product by inhalation or spillage) using the EIU form. This must be done irrespective of whether an AE has occurred and within 24 hours of

awareness of the pregnancy. The information submitted should include the anticipated date of delivery (see following information related to induced termination of pregnancy).

Follow-up is conducted to obtain pregnancy outcome information on all exposure during pregnancy reports with an unknown outcome. The Investigator will follow the pregnancy until completion or until pregnancy termination (e.g., induced abortion) and then notify the Sponsor or its designated representative of the outcome as a follow-up to the initial EIU form. In the case of a live birth, the structural integrity of the neonate can be assessed at the time of birth. In the event of a termination, the reason(s) for termination should be specified and, if clinically possible, the structural integrity of the terminated fetus should be assessed by gross visual inspection (unless pre-procedure test findings are conclusive for a congenital anomaly and the findings are reported).

If the outcome of the pregnancy meets the criteria for immediate classification as an SAE (e.g., ectopic pregnancy, spontaneous abortion, intrauterine fetal demise, neonatal death, or congenital anomaly [including that in a live born, a terminated fetus, an intrauterine fetal demise, or a neonatal death]), the Investigator should follow the procedures for reporting SAEs.

Additional information about pregnancy outcomes that are classified as SAEs follows:

- “Spontaneous abortion” includes miscarriage and missed abortion.
- All neonatal deaths that occur within 1 month of birth should be reported, without regard to causality, as SAEs. In addition, infant deaths after 1 month should be reported as SAEs when the Investigator assesses the neonatal death as related to exposure to investigational product.

Additional information regarding the exposure during pregnancy may be requested by the Investigator. Follow-up information regarding the outcome of the pregnancy and any postnatal sequelae in the infant will be required.

